## 6 TRIAL DESIGN

In Part 1, approximately 77 subjects will be randomized in a 1:1:1 ratio to the following dose groups:

- **Zimura™ 1 mg/eye**
- **Zimura™ 2 mg/eye**
- **Sham**

Commencing with Amendment C, no new subjects will be enrolled in Part 1 of this trial as recruitment has been completed for Part 1.

In Part 2, approximately 200 subjects will be randomized in a 1:2:2 ratio to the following dose groups:

- **Zimura™ 2 mg/eye + Sham**
- **Zimura™ 4 mg/eye (administered as two injections of Zimura™ 2 mg)**
- **Sham + Sham**

Subjects will receive monthly intravitreal injections of Zimura™ and/or Sham for 18 months.

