### **7.2 Tonometry**

Tonometry will be performed at all time-points specified in Section 10.2 “Trial Assessments”. On days when two injections are given, the second injection may not be administered until the IOP is  $\leq 21$  mmHg or within 5 mmHg of the pre-injection IOP, at which time the IOP is recorded. After the second injection and also

on days with only one injection, the IOP should be measured and recorded at least 30 minutes after the injection and IOP must be < 30 mmHg before the subject leaves the clinic. For the post-injection tonometry, proper care should be taken to minimize the risk of contamination.

Goldmann applanation tonometry must be performed at Screening and pre-injection on Day 1, Months 6, 12, 18, and Early Withdrawal. Tono-Pen may be used at all other timepoints. Goldmann applanation tonometry must also be used to verify intraocular pressure (IOP) reading of  $\geq 30$  mmHg occurring at any time.

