### 9.1.2 Treatment Regimen and Duration

Subjects randomized to active drug or Sham will receive monthly injections of Zimura™ or Sham for 18 months. Monthly doses should be administered at least 21 days apart.

- Part 1 Subjects:
  - Subjects randomized to the Zimura™ 1 mg/eye treatment arm will receive Zimura™ 1 mg/eye (50 µL) intravitreal injection.
  - Subjects randomized to the Zimura 2 mg/eye treatment arm will receive Zimura™ 2 mg/eye (100 µL) intravitreal injection.

- Subjects randomized to the Sham treatment arm will receive Sham injections.
- Commencing with Amendment C, no new subjects will be enrolled in Part 1 of this trial. Subjects in Part 1 who have received greater than or equal to 18 months of Study Drug treatment will be discontinued from the study after Amendment C.
- Part 2 Subjects:
  - Subjects randomized to the Zimura™ 2 mg/eye treatment arm will receive a Zimura™ 2mg/eye injection (100 µL) and a Sham injection
  - Subjects randomized to the Zimura™ 4 mg/eye treatment arm will receive two injections of Zimura™ 2 mg/eye. The injection volume for subjects randomized to this arm will be of (100 µL) per injection.
  - Subject's randomized to the Sham treatment arm will receive 2 Sham injections.

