### **Post-injection**

- Ophthalmologic Examination - at least 30 minutes after the last (whether first or second) injection (SE)
- Tonometry (SE):
  - If one injection is administered (including sham):
    - The IOP should be recorded at least 30 minutes after the injection.
  - If two injections are administered (including sham):
    - The second injection may NOT be administered until the IOP is  $\leq 21$  mm Hg or within 5 mm Hg of the baseline IOP on the day of injection, at which time the IOP will be recorded.
    - The IOP should be recorded at least 30 minutes after the 2nd injection.

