### 8.5 **OPHTHALMIC VARIABLES**

**Ophthalmic Examination.** The following ophthalmic examination variables will be analysed by shift table from Baseline to the pre-injection examination on Month 12 or last visit available whichever comes later (normal/abnormal, unless otherwise specified below).:

- Examination of the motility
- Inspection of the lids/lacrimal/lashes
- Examination of the conjunctiva/sclera
- Inspection of the cornea
- Examination of the iris
- Examination of the pupils
- Inspection of the lens status (aphakic, pseudo-phakic, phakic; if phakic, nuclear/PSC/cortical 0, 1, 2, 3, 4), including a listing of subjects with a change in lens status for study eye and (separately) for fellow eye
- Examination of the posterior vitreous detachment
- Inspection of the optic nerve
- Inspection of the macula
- Examination of the retinal vessels

The following ophthalmic examination variables will be analysed by shift table from Baseline through Month 12 or last visit available whichever comes later, on a monthly basis (normal/abnormal, unless otherwise specified below), and from pre-injection to post-injection at each monthly injection

- Examination of the anterior chamber activity: Cells (0, trace, 1+, 2+, 3+, 4+)
- Inspection of the vitreous haze (0, 1+, 2+, 3+, 4+)
- Examination of the vitreous haemorrhage

• Examination of peripheral retina

**Intraocular Pressure.** IOP will be summarized by visit, including all pre-injection, "IOP after first injection" and "IOP after second injection" measurements. An additional tabular summary of the percentage of subjects in categories of IOP will be presented by treatment group, visit, and injection time (pre-injection, IOP after first injection, IOP after second injection).

"IOP after injection" is defined as the IOP measurement that is closest in time to the protocolspecified post-injection timepoint (but at least 25 minutes post-injection). If there are two closest measurements equidistant to this timepoint, then the measurement after the protocol-specified timepoint will be used.

Mean IOP over time of all scheduled measurements (pre-injection, IOP after first injection, and IOP after second injection) will be plotted.

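### The 25-minute minimum in SAP 8.5 does not fit the Part 2 IOP reading taken between two injections, so the after-first-injection summaries can be empty, duplicated or selective

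*SAP*

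**What the plan says.** **SAP 8.5 (Intraocular Pressure)** has one definition for IOP after injection: "the IOP measurement that is closest in time to the protocolspecified post-injection timepoint (but at least 25 minutes post-injection". The category table is broken down "by treatment group, visit, and injection time (pre-injection, IOP after first injection, IOP after second injection". The plot uses the same readings: "Mean IOP over time of all scheduled measurements (pre-injection, IOP after first injection, and IOP after second injection) will be plotted". No separate definition is given for a reading taken between two injections.

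**Protocol 7.2** has two timing rules. After the second of two injections, and "on days with only one injection, the IOP should be measured and recorded at least 30 minutes after the injection", there is a clock time. Between two injections there is none: the second injection waits until pressure is at or below 21 mmHg or "within 5 mmHg of the pre-injection IOP, at which time the IOP is recorded". The post-injection instructions for the dosing visits in Protocol 10.2.3 repeat this, under the condition "If two injections are administered (including sham".

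**Who is affected.** Protocol 6 states: "In Part 2, approximately 200 subjects will be randomized in a 1:2:2 ratio to the following dose groups". Under Protocol 9.1.2 all three of those groups have two injections per dosing visit. For the control group, "Subject's randomized to the Sham treatment arm will receive 2 Sham injections". Part 1 subjects have one injection per visit.

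**The concern.** One selection rule, built around a clock time, is applied to two readings, and only one of them has a clock time. The between-injection reading is triggered by a pressure level. A rule that discards anything earlier than 25 minutes will discard it whenever pressure settles, and is recorded, sooner than that.

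IOP is a named safety endpoint, and 4 mg is the only arm with two active injections per visit, so readers will look at these rows for that arm. SAP 8 bars imputation of safety data and uses observed cases. Excluded readings would therefore drop out of the table and plot and leave a subset chosen by elapsed time. SAP 3.4.1 builds tables by treatment arm, not by Part, so readings of different kinds would share a column.

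**Working it through.** The plan gives no figure to reproduce here. The check applies the SAP rule to the two readings the protocol schedules at a two-injection visit.

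**1. Selection rule.** Let *t* be the minutes from the first injection to the between-injection reading (A). Assume the second injection follows 1 minute later and its reading (B) comes 30 minutes after that, the earliest the protocol allows. B then falls *t* + 1 + 30 = *t* + 31 minutes after the first injection. Values of *t* from 0 to 60 were tried.

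| *t* (minutes) | Only readings before the second injection are candidates | Candidates not limited |
|---|---|---|
| 0 to 24 | No eligible reading; cell empty | B chosen (31 to 55 minutes after the first injection); repeats the second-injection value |
| 25 to 60 | A chosen | A chosen |

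The result is the same whether the target time is 30 minutes or the moment the criterion is met. With a 30-minute target and *t* = 25, A is 5 minutes from target and B is 26. With the target at *t*, A is the closest reading by definition but is still removed when *t* < 25.

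**2. Share affected.** The documents give no times. The figures below assume a distribution for the time of recording, with mean *m*:
- exponential: P(*t* ≥ 25) = exp(−25/*m*)
- lognormal, CV 0.5: 1 − Φ((ln 25 − μ)/σ), with σ² = ln 1.25 and μ = ln *m* − σ²/2

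| Assumed mean (minutes) | Exponential | Lognormal |
|---|---|---|
| 5 | 0.7% | 0.0% |
| 10 | 8.2% | 1.5% |
| 20 | 28.7% | 23.9% |
| 30 | 43.5% | 56.0% |
| 45 | 57.4% | 84.3% |

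The share of between-injection readings that would be eligible runs from about 0% to 84%, depending on the assumption. This shows only that the documents do not settle the share.

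**3. What an eligible reading can show.** With pre-injection pressure *P*, and taking the 5 mmHg limit as inclusive, the highest value that meets the criterion is max(21, *P* + 5). From *P* = 12 a reading of 21 passes (rise of 9); from *P* = 22 a reading of 27 passes (rise of 5). If the criterion is followed, no recorded value can be both above 21 mmHg and more than 5 mmHg above pre-injection. In Part 1 the reading is taken at 30 minutes or later and its recording does not depend on reaching a pressure level.

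**4. Mixing within columns.** Using the planned numbers in Protocol 11.3, Part 1 single-injection subjects make up:
- 2 mg: 26/(26 + 40) = 26/66 = 39%
- Sham: 26/(26 + 80) = 26/106 = 25%
- 4 mg: 0/80 = 0%

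**The case against.** The best defence is that the 25-minute condition was written for readings that have a clock time. SAP 8.5 also says all first- and second-injection measurements will be summarised and keeps the two labels apart. A programmer might therefore use the between-injection value as recorded and never file a later reading under the first injection. That is a sensible intention, and it makes the duplicate outcome less likely than the empty cell. But the text defines the term once, uses it for both injections, and exempts neither from the minimum. Using the reading as recorded would depart from the written rule.

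Other points on that side stand:
- Parts of Protocol 9.1.3 and the appendices are redacted, and the assessments chart and the contents of the SAP appendix are not available. The claim is limited to the visible text.
- A reader might infer that only slow-recovering eyes contribute. That does not follow. The protocol sets no checking interval, so an eye that settles at 5 minutes may be read at 25. Selection is on time of recording.
- A reader might infer that the between-injection value cannot show a rise. It can, as the step from 12 to 21 mmHg shows; the criterion limits the rise and does not remove it.
- SAP 3.4.1 lists the time and method of tonometry among the CRF data for listings, and increased intraocular pressure is counted among ocular adverse events. These keep the information available but do not repair the table or the plot.

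**Conclusion.** The mismatch is real and confined to the after-first-injection cells and plot points for Part 2 dosing visits. There, the SAP rule as written excludes or misassigns any between-injection reading taken before 25 minutes. Separately, the 2 mg and Sham columns combine Part 1 and Part 2 readings of different kinds, while 4 mg has only the kind limited by the clearance criterion.

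It would be tempting to say that the Part 2 IOP table as a whole is empty or biased, or to quote a percentage of lost readings. The documents support neither. Pre-injection, second-injection and Part 1 readings fit the rule, and the share lost depends on recording times that the documents do not give. The summaries are descriptive and the primary endpoint is not involved. The correction is still worth making, because Protocol 11.6.1 requires analysis details to be fixed before unmasking and the present wording gives a wrong safety summary if followed. The conclusion assumes that no unseen text sets a minimum time for the between-injection reading.

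**What to change.** In SAP 8.5:

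1. Keep the 25-minute minimum only for the reading after the last injection of the visit (the single injection in Part 1, the second in Part 2).
2. Define the Part 2 between-injection reading separately, as the IOP recorded at clearance for the second injection, with no minimum time and limited to readings before that injection.
3. Summarise its elapsed time since the first injection, from the tonometry times on the CRF.
4. Do not pool it with Part 1 single-injection readings in any row, column or plotted mean.
5. If last-injection readings are compared across arms, show them by Part. Note that in Part 2 the last injection is a sham in the 2 mg arm, because Protocol 11.5 has the active injection given first, and is active in the 4 mg arm. That comparison therefore has its own limitation.

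The cost is SAP wording and table layout, with no new data collection. No change to the clinical IOP rule is proposed.

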## 8.6 CLINICAL LABORATORY DETERMINATION

- All laboratory data will be listed and values falling outside normal ranges will be identified, whether they will be deemed clinically relevant or not.
- Laboratory data will also be summarized in tables presenting values at each scheduled visit up through the month 12 visit
- Value changes from Baseline to each scheduled visit up through the month 12 visit
- A summary table of all analytes with the Baseline mean and the mean change from Baseline to the last value observed
- A summary table of all analytes with the Baseline median and the median change from Baseline to the last value observed

for the following parameters: hematological parameters (hemoglobin, white blood cells, platelets, neutrophils (absolute numbers), lymphocytes (absolute numbers), monocytes (absolute numbers), eosinophils (absolute numbers), basophils (absolute numbers), renal function parameters (serum creatinine and BUN), hepatic function parameters (serum bilirubin, alkaline phosphatase, GGT, SGOT/AST and SGPT/ALT), electrolytes (sodium, potassium, chloride, bicarbonate, calcium and phosphate), urinalysis parameters (complete urinalysis including specific gravity, protein, blood, etc.).

The incidence of subjects with "Notable Laboratory Values" after the first dose of study drug will be evaluated using the criteria for Notable Laboratory Values given below. Only data collected in the first year after the first dose of study drug, up to the laboratory data taken at the Month 12 visit (before Month 12 treatment is administered) will be included; if there is no Month 12 visit, data will be included up to a target of 365.25 days after date of first dose, or 30 days after the last dose of study drug, whichever is later.

By-subject listings of all notable laboratory values will also be provided; for each subject who has an analyte with a notable value, all values of that particular analyte taken during the study will be presented in the listing, and the notable value, and any values outside of normal limits, will be identified.

For this "Notable Laboratory Values" analysis, *all* laboratory values after randomization will be taken in account, i.e., any values obtained after Day 1, at unscheduled visits, as well as values from the regularly scheduled laboratory visit at Month 12. Three Notable Laboratory Values tables and accompanying by-subject listings will be presented: (1) notable abnormalities for subjects with normal Baseline results, (2) notable abnormalities for subjects with abnormal Baseline results and (3) notable abnormalities without regard to Baseline abnormalities (i.e., normal or abnormal Baseline results). The table without regard to Baseline abnormalities will be a composite of the previous two tables (normal Baseline, abnormal Baseline).

Lab analytes and primary criteria used for Notable Laboratory Values:

### a. HEMATOLOGY

- i. Hemoglobin < 0.75x Baseline
- ii. Platelets  $< 75 \text{ or} > 750 (10^9/L)$
- iii. WBC count  $< 2.5 \text{ or} > 17.5 (10^9/L)$
- iv. Neutrophils (absolute) < 0.5x LLN or > 1.5xULN
- v. Eosinophils (absolute) > 1.5xULN
- vi. Lymphocytes (absolute) < 0.5x LLN or > 1.5xULN

### b. LIVER FUNCTION

- i. Total bilirubin > 1.5xULN
- ii. Alkaline phosphatase > 1.5xULN
- iii. ASAT (SGOT) > 3xULN
- iv. ALAT (SGPT) > 3xULN
- v. GGT > 3xULN
- c. RENAL FUNCTION
  - i. BUN > 1.3xULN
  - ii. Creatinine > 1.3xULN
- d. ELECTROLYTES
  - i. Potassium < 0.9xLLN or > 1.1xULN
  - ii. Sodium < 0.9xLLN or > 1.1xULN

- iii. Chloride < 0.9xLLN or > 1.1xULN
- iv. Carbon dioxide < 0.9xLLN or > 1.1xULN
- v. Calcium < 0.9xLLN or > 1.1xULN
- vi. Phosphorus < 0.9xLLN or > 1.1xULN

Notable abnormalities for subjects with abnormal Baseline results are subject to the primary criteria above and the following secondary criteria:

### a. HEMATOLOGY

- i. Hemoglobin < 0.75x Baseline (same as primary criterion)
- ii. Platelets < 0.75x Baseline or > 1.25x Baseline
- iii. WBC count < 0.75 Baseline or > 1.25x Baseline
- iv. Neutrophils (absolute) < 0.5x Baseline or > 1.5x Baseline
- v. Eosinophils (absolute) > 1.5x Baseline
- vi. Lymphocytes (absolute) < 0.5x Baseline or >1.5x Baseline

### b. LIVER FUNCTION

- i. Total bilirubin > 1.5x Baseline
- ii. Alkaline phosphatase > 1.5x Baseline
- iii. ASAT (SGOT) > 1.5x Baseline
- iv. ALAT (SGPT) > 1.5x Baseline
- v. GGT > 1.5x Baseline

### c. RENAL FUNCTION

- i. BUN > 1.3x Baseline
- ii. Creatinine > 1.3x Baseline

### d. ELECTROLYTES

- i. Potassium < 0.9x Baseline or > 1.1x Baseline
- ii. Sodium < 0.9x Baseline or > 1.1x Baseline
- iii. Chloride < 0.9x Baseline or > 1.1x Baseline
- iv. Carbon dioxide < 0.9x Baseline or >1.1x Baseline
- v. Calcium < 0.9x Baseline or >1.1x Baseline
- vi. Phosphorus < 0.9x Baseline or > 1.1x Baseline

### 8.7 ECG

ECG results will be tabulated at Baseline as "normal", "abnormal, not clinically significant" or "abnormal, clinically significant". At follow-up visits, ECG results will be tabulated as "no change from Baseline", "NOT clinically significant change from Baseline" or "clinically significant change from Baseline". A by-patient listing will be provided for ECGs which are deemed clinically significant.

Continuous data (heart rate; PR, QRS, QT and QTc intervals) will be summarized using mean, standard deviation, median, minimum and maximum values at each scheduled visit, and change from Baseline at each visit.

### APPENDICES
